13.5 EXCESSIVE HEMATOPOIESIS

Time to initial onset of potential Excessive Hematopoiesis, regardless any use of rescue therapy, will be analyzed based on Hb central lab

The presence of potential EH will be defined as either:

- Hb increase by >2.0 g/dL between any 2 visits within 4 weeks of treatment, or
- at least one Hb value >13 g/dL during the treatment period.

Each of these two criteria will be analyzed separately. Time to first occurrence of potential EH (for either criterion separately) regardless the use of rescue therapy during the treatment period will be defined in weeks as $:(\text{First event date} - \text{Analysis date of first dose} + 1) / 7$

where ‘First event date’ is defined as first date of occurrence of the criterion met during the treatment period.

For a subject without potential EH, the time to censoring will be calculated (in weeks) as:

$$(\text{Date of last hemoglobin assessment during the treatment period} - \text{Analysis date of first dose} + 1) / 7$$

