4.6.2.1 Red Blood Cell Transfusion

Red blood cell (RBC) transfusion is allowed if rapid correction of anemia is required to stabilize the patient's condition (eg, acute hemorrhage) or the Investigator is of the opinion that the blood transfusion is a medical necessity. Study drug treatment may continue during or after RBC transfusion administration.

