4.6.2.2 Erythropoiesis-Stimulating Agent (ESA)

Use of *more than two* courses of ESA for anemia rescue is a withdrawal criterion requiring early termination from study treatment. Nevertheless, criteria are provided in order to standardize the use of ESA rescue. The Investigator should consider initiating use of an approved ESA only if all of the following criteria are met:

- The subject's Hb level has not sufficiently responded to two or more dose increases or maximum doses (by body weight) of the study drug; **and**
- The subject's Hb is < 8.0 g/dL; **and**
- Reducing the risk of alloimmunization in transplant eligible subjects and/or reduction of other RBC transfusion-related risks is a goal

ESA treatment must be stopped after 4 weeks of use or when Hb \geq 9 g/dL is reached, whichever occurs first. Study drug treatment may be resumed after the following intervals:

- Two days after stopping epoetin
- One week after stopping darbepoetin alfa
- Two weeks after stopping methoxy polyethylene glycol-epoetin beta (Mircera)

After two successful courses of rescue with ESA and return to study drug, subjects who again meet the above criteria for ESA rescue and receive a third course of ESA must be discontinued from the study drug at this point. Such a subject will complete procedures for early termination and subsequent modified follow-up according to the procedures outlined in Section 7.1.2.6, if consent is not withdrawn to do so.

Note: ESA administration during hospitalization: Such ESA use is not considered a protocol deviation, if study subjects have no access to study drug while hospitalized.

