12.2.3 Hb Censoring After Rescue Therapy

Because the rescue use may potentially confound the effect of roxadustat, analysis will also be performed where Hb values will be censored for 6 weeks (or 8 weeks if during an evaluation period) after rescue therapy use to examine its potential impact on the robustness of the efficacy findings.

All sensitivity analyses for Change in Hb described in the above section will be applied to these scenarios using the ITT Population.

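### Excessive hematopoiesis is counted regardless of rescue, with no companion analysis: if placebo is rescued more, a roxadustat excess in rapid Hb rises is diluted

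*SAP*

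**What the plan says.** SAP 13.5 sets out the analysis of potential excessive hematopoiesis (EH): "Time to initial onset of potential Excessive Hematopoiesis, regardless any use of rescue therapy, will be analyzed based on Hb central lab". The instruction to disregard rescue is repeated where time to first occurrence is defined. Criterion 1 is "Hb increase by >2.0 g/dL between any 2 visits within 4 weeks of treatment". Criterion 2 is "at least one Hb value >13 g/dL during the treatment period". The section adds: "Each of these two criteria will be analyzed separately". A subject without an event is censored at the "Date of last hemoglobin assessment during the treatment period", so rescue does not end follow-up. SAP 4.4 lists EH as one of three bulleted study-specific safety assessments.

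For efficacy the SAP treats rescue differently from one analysis to another. SAP 12.2.3 adds a rescue-censored analysis and gives the reason: "Because the rescue use may potentially confound the effect of roxadustat". Its window is 6 weeks, or 8 weeks inside an evaluation period. SAP 12 drops Hb values for 6 weeks after rescue for the Ex-US primary endpoint but keeps them for the US primary endpoint.

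Two rescue provisions in the Protocol matter here. On transfusion, section 4.6.2.1 says: "Study drug treatment may continue during or after RBC transfusion administration". On ESA rescue, section 4.6.2.2 requires Hb below 8.0 g/dL at entry, and "ESA treatment must be stopped after 4 weeks of use or when Hb" has reached 9 g/dL, whichever comes first.

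**The concern.** The safety question behind EH is whether study drug raises Hb too fast or too high. A transfusion raises Hb for another reason, yet its effect on Hb can meet criterion 1. Because study drug may continue after transfusion, the post-transfusion value falls in the treatment period and is counted.

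This is not neutral between arms. SAP 12.3 (items 6 and 9) tests roxadustat for superiority on time to rescue and time to transfusion, so the plan anticipates more or earlier rescue on placebo. Rescue-driven events would then fall mainly on placebo and narrow any roxadustat excess. Keeping post-rescue values works against roxadustat in the US efficacy comparison, because rescue raises placebo Hb. In the EH comparison the same choice works in roxadustat's favour. SAP 13.5 plans nothing that would let a reader separate the two sources of events.

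**Working it through.** **Figure to reproduce.** There is none. The documents give no EH rate, rescue rate, event count, power or margin for EH, and 13.5 names no test or effect measure.

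**Reading of criterion 1.** I take it as any two visits no more than 4 weeks apart, which is how Protocol Appendix 1 describes the corresponding dose-reduction trigger.

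**Which criterion is exposed.**
- ESA rescue starts below 8.0 g/dL and stops at 9 g/dL or 4 weeks. A rise of more than 2.0 g/dL that ends at the 9 g/dL stop needs a start below 9 − 2 = 7 g/dL; otherwise it needs an overshoot. Criterion 2 lies 13 − 9 = 4 g/dL above the stop level, so ESA rescue should rarely cause it.
- Transfusion has no Hb limit in Protocol 4.6.2.1. It is the likelier cause of a criterion 1 event, and some effect on criterion 2 cannot be excluded.

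**Illustrative model for criterion 1.** Let d be the risk of an event not caused by rescue, r the share of subjects rescued, and f the share of rescued subjects whose Hb rises by more than 2.0 g/dL within 4 weeks because of rescue. Take f as equal in both arms and the two causes as independent. The counted risk is

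P = 1 − (1 − d)(1 − r·f).

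The counted difference, roxadustat (R) minus placebo (P), is

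(dR − dP) − f·[(1 − dP)·rP − (1 − dR)·rR].

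When placebo is rescued more (rP > rR), dR ≥ dP and f > 0, the bracket is positive, so the excess always shrinks. It reverses only if f exceeds

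f* = (dR − dP) / [(1 − dP)·rP − (1 − dR)·rR].

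**Inputs, all assumed.** d of 5% v 1%, 10% v 1%, 15% v 2% and 20% v 2%; r of 5% v 15%, 8% v 30% and 10% v 40% (roxadustat v placebo throughout); f of 10%, 25% and 50%. That makes 4 × 3 × 3 = 36 scenarios.

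**Two worked cases** with rescue 8% v 30% and f = 25%:
- d 10% v 1%: roxadustat 1 − 0.90 × 0.98 = 11.8%; placebo 1 − 0.99 × 0.925 = 8.4%.
- d 5% v 1%: roxadustat 1 − 0.95 × 0.98 = 6.9%; placebo again 8.4%. The direction reverses.

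| d (R v P) | r (R v P) | f | Counted (R v P) | Difference in points, true → seen | Risk ratio, true → seen |
|---|---|---|---|---|---|
| 20% v 2% | 5% v 15% | 10% | 20.4% v 3.5% | 18 → 16.9 | 10 → 5.88 |
| 10% v 1% | 8% v 30% | 25% | 11.8% v 8.4% | 9 → 3.4 | 10 → 1.40 |
| 5% v 1% | 8% v 30% | 25% | 6.9% v 8.4% | 4 → −1.5 | 5 → 0.82 |
| 5% v 1% | 10% v 40% | 50% | 9.8% v 20.8% | 4 → about −11 | 5 → 0.47 |

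**All 36 scenarios.** The excess shrinks in every one and reverses in 8. True risk ratios of 5 to 10 are seen as 0.47 to 5.88.

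**Break-even f\*.** For d 5% v 1% and rescue 10% v 40%, f* = 0.04 / (0.396 − 0.095) = 0.13. For d 10% v 1% and rescue 5% v 15%, f* = 0.09 / (0.1485 − 0.045) = 0.87. With rescue 5% v 15% and d of 15% v 2% or 20% v 2%, f* is above 1 (0.13 / 0.1045 and 0.18 / 0.107), so no value of f reverses the comparison.

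**Without post-rescue values** the model returns to d, provided that dropping those values is non-informative.

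**The case against.** The SAP states the rule openly, twice, and labels the events as potential EH. As an all-cause count it is legitimate. It agrees with the US primary analysis, which also keeps post-rescue Hb, and with the dose-reduction trigger in Protocol Appendix 1, which has no rescue exception. Replacing it would carry its own risk. Rescue follows low Hb, so removing post-rescue values may be informative. Study drug may also continue after transfusion or IV iron, so genuine drug-driven rises would be lost. All of this stands, and it is why the stated analysis should stay. It does not explain why that analysis should stand alone.

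Three stronger readings are tempting, and the documents do not support them:
- A reader might infer that more rescue on placebo hides or reverses a roxadustat excess as a matter of course. Dilution follows in the model, but reversal occurred in only 8 of 36 assumed scenarios, and a large excess with modest rescue stays plain (20.4% v 3.5%).
- A reader might infer that EH as a whole is compromised. Criterion 2 is analysed separately and gives a largely unaffected view of Hb that goes too high.
- A reader might infer that a planned test would give a false finding for roxadustat. Section 13.5 names no test, hazard ratio or margin, so error rates or power for such a test would be imported.

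**Conclusion.** The point holds for criterion 1. Rises caused by rescue count as events, and if placebo is rescued more, the comparison is biased against showing a roxadustat excess. The direction rests on two conditions: more rescue on placebo, which the superiority tests anticipate but no stated rate confirms, and at least some rescues being followed by a rise above 2.0 g/dL. The size is unknown. In the assumed scenarios it runs from slight (risk ratio 10 seen as 5.88) to a reversal (5 seen as 0.47), and reversal needs a small true excess or frequent placebo rescue with large rises. Criterion 2 should be little affected. The stated analysis is not wrong as an all-cause summary. What is missing is a companion analysis, without which a null or favourable criterion 1 result could not be attributed to the drug.

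**What to change.** Keep the stated analysis in SAP 13.5 and add, for each criterion and in both arms:

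1. An analysis that excludes Hb values within 6 weeks after transfusion or ESA rescue, which is the window the SAP already uses for efficacy. A rise does not count if its later value falls in that window. The text should say whether the window for an ESA course runs from its first or its last dose.
2. A table of EH events by arm and by whether rescue preceded them.

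Present both versions side by side. If they agree, rescue is not driving the result; if they differ, the table shows where the difference comes from. For criterion 1 the window is long enough: a later value more than 6 weeks after rescue pairs with an earlier value more than 6 − 4 = 2 weeks after it, so the rescue cannot lie between the two.

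The cost is a few lines of SAP text, one derived flag and one table. Protocol 4.6.2 already requires rescue use to be recorded in the eCRF. The downsides are that the exclusion may be informative, and that a few genuine drug-driven rises soon after rescue will appear only in the all-cause version.

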
Protocol Deviation:
 
Text has been added to pre-specify issues that are not considered protocol deviations.
 
Added text reads as follows:
 
A protocol deviation is generally an unplanned excursion from the protocol that is not implemented or intended as a systematic change. The investigator is responsible for ensuring the study is conducted in accordance with the procedures and evaluations described in this protocol and must protect the rights, safety, and welfare of subjects. The investigator should not implement any deviation from, or changes to, the protocol, unless it is necessary to eliminate an immediate hazard to study subjects.
 
Due to the complex study design and standard of clinical practice, the following issues should not be captured and reported as protocol deviations.
 
Given the complexities of the dose adjustment algorithm, and the need to take into consideration various clinical parameters, it is not considered a protocol deviation when study subjects are dosed based on their clinical circumstance, whether or not this is concordant with the roxadustat dosing algorithm, unless it is related to “excessive hematopoiesis” (refer to Section 4.5.1) or “Overdose” (prescribed >3.0 mg/kg per dose).
 
ESA administration in during hospitalization: Such ESA use is not considered a protocol deviation, if study subjects have no access to study drug while hospitalized.
 
.
	
This section was added to align the protocol with a new SOP for protocol templates.
 
Specifically:
 
Various factors, such as discrepancies between HemoCue Hb and Central lab Hb value, Investigator decision etc. can influence dose titration decisions at the time of the visit or after the visit. As a result, the dose prescribed may not exactly match the dose per the dose adjustment algorithm.
 
However, as the stable dose would be achieved through titration, dosing discrepancy when subjects are dosed based on their clinical status is not considered a protocol deviation unless it is related to excessive hematopoiesis (≥ 13.0 g/dL, requires a dose-hold) or overdose (>3.0 mg/kg/dose).
 
Roxadustat subjects may receive ESA while hospitalized, in part due to lack of access to roxadustat while in hospital, and/or as part of hospital standard-of-care of anemia treatment; therefore, ESA administration in such circumstances is not considered a protocol deviation.
	
Section 9.5.1

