9.5.1 Protocol Deviation

Due to the complex study design and standard of clinical practice, the following issues should not be captured and reported as protocol deviations.

- Given the complexities of the dose adjustment algorithm, and the need to take into consideration various clinical parameters, it is not considered a protocol deviation when study subjects are dosed based on their clinical circumstance, whether or not this is concordant with the roxadustat dosing algorithm, **unless** it is related to “excessive hematopoiesis” (refer to Section 4.5.1) or “Overdose” (prescribed >3.0 mg/kg per dose).
- ESA administration in during hospitalization: Such ESA use is not considered a protocol deviation, if study subjects have no access to study drug while hospitalized.

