19 APPENDICES

Appendix 1 Dose Adjustment Algorithm

		CORRECTION PHASE	Maintenance	MAINTENANCE PHASE			
Change in Hb From 4 Wks Prior (g/dL)	(To achieve initial Hb response)	Hb \geq 13.0g/dL		Hb < 10.5 g/dL	Hb 10.5 to 11.9 g/dL	Hb 12.0 to 12.9 g/dL	Hb \geq 13.0 g/dL
< -1.0	↑	Hold, then resume dosing using maintenance phase rules when:	↑	↑	No change	Hold, then resume dosing when: Hb \leq 11.9 g/dL, at a dose that is reduced by two dose steps	
-1.0 to 1.0	↑		↑	No change	↓		
> 1.0	No change	Hb \leq 11.9 g/dL, at a dose that is reduced by two dose steps	No change	↓	↓		

Abbreviations: ↑ = increase; ↓ = decrease; Hb = hemoglobin; wk(s) = week(s).

Dose Increases and Reductions:

Dose increases (↑) and reductions (↓) are preset to dose steps.

The dose steps are as follows:

20, 40, 50, 70, 100, 150, 200, 250, and 300 mg.

Example: A dose increase at a dose of 70 mg results in 100 mg as the new dose. A dose reduction at a dose of 200 mg results in 150 mg as the new dose.

*Note: Subjects who were on the 120 mg dose step prior to Amendment 2 may still use that dose unless/until a dose review requires a change, at which point new dose steps should be implemented.

Contact the Medical Monitor if dose adjustments are required past the limits of the dose steps; ie, 20 or 300 mg.

Note: Maximum dose capped at 3.0 mg/kg per dose or 300 mg, whichever is lower. Subjects on higher maximum doses from previous protocol versions must change to the new maximum dose at the next scheduled visit.

In a subject whose baseline Hb level was < 8.0 g/dL, a dose increase can be made with either a 1 or 2 dose step increase, per Investigator discretion, to minimize the risk of requiring rescue treatment.

Dose Adjustment for Excessive Hematopoiesis:

[figure not shown]
At any time during the Treatment Period:

- If Hb increases by > 2.0 g/dL in \leq 4 weeks (eg, any 4-week time period), the dose should be reduced by one dose step.

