4.4 SAFETY ASSESSMENTS

Study-specific safety will be assessed by evaluating the following:

- AEs, SAEs, and clinically significant laboratory values
- Vital signs, ECG parameters, and clinical laboratory values
- Excessive hematopoiesis

Pooled safety interpretation will also be determined based on analyses of specific cardiovascular-related endpoints derived from adjudicated events pooled across multiple studies in the roxadustat Phase 3 program. The members of an independent adjudication committee blinded to treatment assignment will adjudicate the following events in multiple phase 3 studies: All cause death, MI, stroke, congestive heart failure requiring hospitalization, unstable angina requiring hospitalization, hypertensive emergency, deep venous thrombosis, pulmonary embolism, and vascular access thrombosis.

Various region-specific pooled analyses of composites of these adjudicated events, pooled across multiple studies will be conducted. The analyses of the adjudicated events will be detailed in the region-specific pooled SAP.

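### SAP 13.5 counts high hemoglobin as potential excessive hematopoiesis only above 13 g/dL, while the protocol's dose hold starts at 13.0 g/dL

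*SAP*

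**What the plan says.** SAP Section 4.4 lists "Excessive hematopoiesis" among the study-specific safety assessments. SAP Section 13.5 gives the analysis: "Time to initial onset of potential Excessive Hematopoiesis, regardless any use of rescue therapy, will be analyzed based on Hb central lab". There are two criteria. The rate criterion is "Hb increase by >2.0 g/dL between any 2 visits within 4 weeks of treatment". The level criterion is "at least one Hb value >13 g/dL during the treatment period". The SAP adds: "Each of these two criteria will be analyzed separately". A subject who does not meet a criterion is censored at the last Hb assessment in the treatment period.

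In the protocol, the Appendix 1 dosing table has a column for Hb ≥ 13.0 g/dL in both the correction and the maintenance phase. The action in the correction phase is "Hold, then resume dosing using maintenance phase rules when" Hb has come down to 11.9 g/dL or less, at a dose two steps lower. The maintenance phase has the same hold. The text under the separate excessive-hematopoiesis heading in Appendix 1 shows only the rule on a rise above 2.0 g/dL within 4 weeks. A figure is missing at that place in the copy reviewed.

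The protocol's summary of changes, in the rationale for the deviation text of Section 9.5.1, speaks of "excessive hematopoiesis (≥ 13.0 g/dL, requires a dose-hold". That is the one place where the hold level and the term are joined explicitly.

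**The concern.** The safety analysis uses a strict inequality at the value where the protocol's hold uses an inclusive one, and neither document says why. A central-lab reading of exactly 13.0 g/dL lies in the range where the protocol would stop dosing, yet it is not an event in the analysis meant to show how often Hb rose too far. The error runs one way: the strict sign can lose events or date them later, and it can never add events or date them earlier. For a listed safety assessment analyzed as time to first onset, that is the less cautious direction.

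**Working it through.** The plan gives no figure on this point, so there is nothing to reproduce. The check sets the texts side by side and follows single subjects through the rule.

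**Inputs**
- Level cut-off in the analysis: Hb > 13 g/dL, central lab (SAP 13.5).
- Hold in the dosing table: Hb ≥ 13.0 g/dL, both phases (Protocol Appendix 1).
- Onset in weeks: (first event date − first dose date + 1) / 7 (SAP 13.5).
- Visits: Weeks 1 and 2, every 2 weeks from Week 4 to Week 24, then every 4 weeks from Week 28. The window is ±2 days through Week 24 and ±3 days from Week 28 (Protocol 7.1.2.2 to 7.1.2.4).
- Assumption: Hb is reported to 0.1 g/dL, as the Appendix 1 bands are written. With finer reporting, fewer values equal 13.0.

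**Boundary.** 13.0 > 13 is false; 13.0 ≥ 13.0 is true. At 0.1 g/dL resolution the two rules disagree at this one value only.

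**Does the rate criterion bring the value back?** No. A subject who reached 13.0 by a fast rise may be an event under the rate criterion, but the two criteria are analyzed separately, so the level analysis still omits that subject. The rate criterion itself agrees with Appendix 1.

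**Effect per subject in the level analysis**

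| Central-lab Hb on treatment | Rule > 13 (SAP) | Rule ≥ 13.0 |
|---|---|---|
| Highest value 12.9 or lower | censored | censored |
| Highest value exactly 13.0 | censored | event at the first 13.0 |
| 13.0 first, above 13 later | event at the later date | event at the first 13.0 |
| Above 13 before, or without, any 13.0 | event | same event, same date |

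**Length of the delay in the third row**, if the next scheduled value is the one above 13:
- Week 12 to Week 14: Day 85 gives 85/7 = 12.14 weeks and Day 99 gives 99/7 = 14.14 weeks, a delay of 2.0 weeks. With windows, 14 ± 4 days = 10 to 18 days = 1.4 to 2.6 weeks. The nominal 2 weeks applies between visits from Week 2 to Week 24.
- Week 28 to Week 32: Day 197 gives 197/7 = 28.14 weeks and Day 225 gives 225/7 = 32.14 weeks, a delay of 4.0 weeks. With windows, 28 ± 6 days = 22 to 34 days = 3.1 to 4.9 weeks.
- The step from Week 24 to Week 28 is also nominally 4 weeks (28 ± 5 days = 23 to 33 days = 3.3 to 4.7 weeks). The step from Week 1 to Week 2 is nominally 1 week.

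An unscheduled central-lab value can shorten any of these. A longer run of readings at 13.0 or below lengthens them.

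**Opportunities.** Scheduled post-dose central-lab Hb through Week 52: 2 (Weeks 1 and 2) + 11 (Weeks 4 to 24) + 7 (Weeks 28 to 52) = 20 values per subject who stays on treatment. This counts the chances for a reading of 13.0; it does not estimate how often one occurs.

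**The case against.** The strongest reply is that there is no protocol definition for the SAP to contradict. In the visible operative text the ≥ 13.0 hold belongs to the titration table, while excessive hematopoiesis is tied to a fast rise and a dose reduction. Protocol Section 2.8 says that doses may be held for excessive hematopoiesis but gives no number. The explicit link stands only in an amendment rationale, which can show intent but cannot serve as the governing text. All of this stands. A reader might infer that SAP 13.5 conflicts with the protocol's own definition; the documents do not support that, and the missing figure in Appendix 1 rules out any claim about what its excessive-hematopoiesis heading leaves out.

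The second reply is that the two cut-offs do different jobs. Dosing follows HemoCue readings (Protocol 4.5.2.1 and 7.4.1), whereas SAP 13.5 is a central-lab category for *potential* events, fixed in advance and applied alike to both arms. This also stands: the analysis does not measure compliance with the hold, before or after the change. It does not explain the strict sign, though. The hold at 13.0 is the only Hb-level hold in the protocol and the evident anchor for the SAP's figure of 13, and equal treatment of the arms does not recover the omitted events.

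A reader might also infer that dosing through the hold goes unrecorded. The waiver in Protocol 4.5.2.2 and 9.5.1 excuses off-algorithm dosing unless "it is related to “excessive hematopoiesis” (refer to Section 4.5.1"), and Section 4.5.1 states no such threshold. The documents do not support that reading either. Section 4.5.2.1 sends the reader to Appendix 1 for excessive hematopoiesis, Sections 7.1.2.2 to 7.1.2.4 do the same for dose review, and HemoCue values are kept in the CRF. What remains is an imprecise section number, an editorial matter outside this point.

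**Conclusion.** The point holds as a minor one, with high confidence in the text comparison. SAP 13.5 leaves a central-lab Hb of exactly 13.0 g/dL out of its level analysis, although that value lies within the protocol's hold range, and no reason is given.

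The direction is certain: events are lost or dated later, never the reverse. The size is unknown. The documents give no distribution of on-treatment Hb; the standard deviation of 1.2 g/dL in the sample-size sections is a power assumption for the difference in mean Hb, and it cannot be turned into a share of subjects whose readings stop at 13.0. A reader might infer a sizeable under-count; the documents offer no basis for a percentage, and none is claimed.

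No efficacy result, dosing rule or analysis set is affected. SAP Table 2, which guides exclusion from the per-protocol set, does not list departure from the dosing algorithm. The conclusion rests on Hb being reported to 0.1 g/dL.

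**What to change.** In SAP 13.5, change the level criterion from > 13 g/dL to ≥ 13.0 g/dL and leave the rate criterion as it is. If the sponsor prefers the strict cut-off, one sentence giving the reason would do.

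The cost is one symbol in the SAP. The downside is slightly higher reported rates of potential excessive hematopoiesis and some earlier onset dates.

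As a separate editorial correction at the next protocol revision, the waiver in Sections 4.5.2.2 and 9.5.1 should cite Appendix 1 in place of Section 4.5.1, as Section 4.5.2.1 already does.
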